## 11.5 Study Centers

There will be approximately 50-60 study sites in the United States (US) and Canada.

The primary and secondary efficacy endpoints will be summarized by study site using descriptive statistics. Exploratory analyses of the primary and secondary endpoints may be performed to elucidate any identified sources of heterogeneity in the results.

## 11.6 Multiple Comparisons

Multiple comparisons of the secondary endpoints will be controlled using the Fixed-Sequence method. Hypotheses testing for the secondary efficacy endpoints will only be conducted if the primary efficacy endpoint has demonstrated statistical significance at 0.05 two-sided in favor of tapinarof. Testing of the secondary endpoints will be performed sequentially following the below pre-specified order (see details in Section 12.7.2):

- Proportion of subjects with  $\geq 75\%$  improvement in PASI from Baseline at Week 12
- Proportion of subjects with a PGA score of 0 or 1 at Week 12
- Mean change in %BSA affected from Baseline to Week 12
- Proportion of subjects with  $\geq 90\%$  improvement in PASI score from Baseline to Week 12

Hypothesis testing for secondary endpoints will stop if statistical significance at 0.05 two-sided in favor of tapinarof is not observed.

## 12. STATISTICAL EVALUATION

### 12.1 Subject Disposition

The number and percentage of subjects screened, screen failed along with reason for screen failures, randomized, included in each analysis population, completing 12-Week Double-Blind treatment, completing the study, withdrawing from treatment (together with the reasons for withdrawal), withdrawing from the study (together with the reasons for withdrawal), and subjects

excluded from PP population (together with the reasons for exclusion) will be summarized using frequencies and percentages by treatment group. For subjects who have completed the 12-Week treatment, the number and percentage of those who elect to enroll in the open-label study will be summarized.

Enrollment and disposition will be listed by subject. Screen failures and subjects not randomized will also be listed by subject.

The number of days in the study (date of study completion / discontinuation minus date of Day 1 plus 1) will be summarized descriptively by treatment group.

## **12.2 Protocol Deviations**

Protocol deviations will be listed by subject. Protocol deviation categories (major vs minor) will be summarized by treatment group.

## **12.3 Demographic and Baseline Characteristics**

Demographics and baseline characteristics will be summarized overall and by treatment for the ITT, PP and Safety populations. The following demographic and baseline variables will be included:

- Age
- Gender
- Race
- Ethnicity
- Weight
- Height
- BMI
- Baseline PGA
- Baseline PASI score
- Baseline %BSA Affected

## **12.4 Study Medication Exposure and Compliance**

The following exposure and compliance parameters will be summarized descriptively by treatment group:

- Total number of days exposed, defined as date of last dose of study drug minus date of first dose of study drug plus 1.

- Number of doses administered, calculated from the subject dose diary. If a subject does not return diary or returns the diary with missing dosing record, the number of doses taken during that period is assumed to be 0.
- Grams (g) of study drug administered, total and average per day. Drug administered is calculated as the summation of the difference between dispensed weight and returned weight for all returned tubes. Unreturned tubes will be assumed unused and will be included as 0 gram in amount drug used calculation.
- Percent compliance will be calculated as the number of doses administered over the number of days exposed.
- Subject compliance, defined as  $\geq 80\%$  compliance over the entire duration of study. If the percentage of study medication compliance is unknown, the subject is assumed to be non-compliant with study medication.

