Investigator Assessed:										
PGA score ^m	X	X	X	X		X		X	X	X
%BSA affected ⁿ	X	X ^o	X	X		X		X	X	X
PASI		X	X	X		X		X	X	X
LTS ^p			X	X		X		X	X	X

Procedures and Assessment	Screening	Baseline	Double-Blind Vehicle-Controlled Treatment Phase						FU ^a	ET ^b
	V 1	V 2	V 3	V 4	P/C ^c	V 5	P/C ^c	V 6	V 7	NA
	Day -34 to Day -1	Day 1	Week 2 D 15 (±2 d)	Week 4 D 29 (±2 d)	Week 6 D 43 (±2 d)	Week 8 D 57 (±2 d)	Week 10 D 71 (±2 d)	Week 12 D 85 (±2 d)	Week 16 D 113 (±4 d)	NA
Completed by Subject:										
DLQI		X		X				X	X	X
SF-36		X		X				X	X	X
PSD		X	X	X		X		X	X	X
LTS			X	X		X		X	X	X
Peak Pruritus NRS ^q		X	X	X	X	X	X	X	X	X
Dispense/collect diary ^f		D	C/D	C/D		C/D		C		C
Review subject diaries for treatment compliance			X	X		X		X		X
Dispense (D)/Collect (C) study drug		D	C/D	C/D		C/D		C		C
Review instructions for study drug application ^s		X	X	X	X	X	X			
Study drug application under supervision ^t		X	X	X		X				
Enrollment (optional) in long-term study								X		

AE = adverse event (s); BMI = body mass index; BSA = body surface area; %BSA = percent of total BSA; D/d = day(s); DLQI = Dermatology Life Quality Index; ECG = electrocardiogram; eCRF = electronic Case Report Form; ET = early termination; FU = follow-up; HADS = Hospital Anxiety and Depression Scale; LTS = Local Tolerability Scale; NA = not applicable; NRS = Numeric Rating Scale; PASI = Psoriasis Area and Severity Index; P/C = phone contact; PGA = Physician Global Assessment; PK = Pharmacokinetics; PSD = Psoriasis Symptom Diary; SF-36 = 36-Item Short Form Survey; V = Visit; WOCBP = women of child-bearing potential.

^a The Follow-Up Visit will be performed for any subject who: (a) prematurely withdraws from the study, (b) fails to qualify for participation in the open-label long-term study, or (c) qualifies to participate in the open-label long-term study but elects not to enroll in that study.

^b Subjects who withdraw from the study before 12 weeks (Visit 6) will complete an Early Termination Visit.

^c Phone calls are scheduled between visits to assess AEs and concomitant medications, to review study drug application procedures, and to confirm subject's continued participation in the study. Subjects should be reminded to complete the diary and bring with them to the next clinic visit.

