^d Medical history will include year of plaque psoriasis diagnosis, CV medical history and risk factors (including height, weight, smoking history, medical conditions, and family history of premature CV disease) and family history of liver disease.

^e Record any changes to medical history.

^f Serum pregnancy test to be performed at the Screening visit only and urine pregnancy test to be performed at subsequent clinic visits.

^g Urine pregnancy test to be performed before randomization.

^h Physical examination will include height, weight, and BMI at the Screening visit; a brief physical examination will be performed at other visits (Section 6.3.2).

- ⁱ Vital signs will include blood pressure, pulse, and body temperature.
- ^j Including serum chemistry and liver chemistry tests, and hematology.
- ^k Photography will be performed in a subgroup of subjects at selected (8 to 10) study centers; this is not required of subjects for participation in the study. Informed consent/assent and photographic release will be required.
- ^l Blood sample collection for PK will be performed at a subset of sites in a subset of subjects. Sample to be collected prior to study drug application in clinic.
- ^m The PGA assessment should be performed before the %BSA and PASI assessments.
- ⁿ The subject's scalp, palms, fingernails toenails, and soles should be excluded from the %BSA calculations.
- ^o %BSA affected calculation should be completed before the PASI assessment. Note that lesions on scalp, palms, fingernails, toenails, and soles will not be included in the calculation of %BSA affected as these areas will be excluded from the efficacy analyses.
- ^p The LTS assessment also consists of a subject-assessed component (Section [6.3.5](#)).
- ^q Subjects should perform the Peak Pruritus NRS assessment daily (Section [6.2.2.4](#)) and record the results in their diary. On study visit days, subjects will not complete the diary at home; application time and NRS will be recorded in the clinic.
- ^r Subjects will be instructed on when and how to complete diaries.
- ^s Subjects will be instructed to apply study drug once daily at the approximate same time each day, based on subject preference (Section [5.1.5](#)).
- ^t At clinic visits, study drug will be applied after safety and efficacy assessments have been conducted (see Section [5.1.5](#) for additional details on timing of application of study drug during clinic visits).

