5.4. Compliance with Study Drug Administration

At baseline, study staff will provide the subject with detailed instructions concerning protocol requirements and use of study drug. Additionally, subjects will be asked to complete a daily diary with the time of each application of study drug. At each post baseline study visit, study staff will review use of study drug, as applicable, with the subject.

When subjects are dosed at the site, they will apply the study drug under supervision of the study staff. The date and time of each dose administered in the clinic will be recorded in the source documents. The study drug and study subject identification will be confirmed at the time of dosing by a member of the study site staff other than the person dispensing the study drug.

At the time of dispensing study drug to each subject, site personnel will weigh the tubes to be dispensed and will record the weight of all tubes dispensed at each visit in the drug accountability logs. Subjects will be instructed to bring all used and unused tubes with them to each study visit. Site personnel will weigh the returned tubes (used and unused) and record the weight in the drug accountability logs. If a tube has been lost, discarded, or forgotten by the subject, then the site personnel will make a notation of this on the drug accountability logs. The site personnel will remind the subject to keep all tubes of study drug dispensed and to bring all used and unused tubes to each clinic visit. These data will be used to estimate subject compliance with use of study drug. Tubes of study medication dispensed at the most recent prior visit which remain unopened (the foil cap on the tube remains fully intact/undisturbed) may be re-dispensed to study subjects at the current visit. Opened, partially used tubes or tubes with foil overlay removed are not to be re-dispensed to study subjects. If there is any question as to re-dispensation, sites should issue new tubes of study medication to the subject(s).

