## 8. ANALYSIS POPULATIONS

The following populations are defined:

- Safety population: All randomized subjects who receive at least 1 application of study drug will be included in the Safety population. Subjects will be analyzed as treated.
- Intent-to-treat (ITT) population: All randomized subjects will be included in the Intent-to-treat population. Subjects will be analyzed as randomized.
- Per Protocol (PP) population: All subjects in the ITT population who did not have any major protocol deviations or other events that may impact the interpretation of the primary efficacy endpoint will be included in the PP population. Exclusion criteria for the PP Population may include:
  - Failure to meet the enrollment inclusion/exclusion criteria
  - On-study use of oral corticosteroids for >3 days and/or at >10mg dose
  - Failure to have a Week 12 assessment that occurs  $\leq 3$  days post last dose and also between study day 78 to 91 (inclusive) for the primary efficacy endpoint. Alternative days post dose and visit window may be used upon review of the actual blinded data before database lock.

- Failure to be compliant with treatment regimen (as defined in Section 12.4, i.e., compliance < 80%)

Additional criteria that may or may not be documented as protocol deviations may be added to determine PP population. The composition of the PP population will be determined and documented in blind reviews of the database conducted prior to unblinding the study database.

The ITT and PP Populations will be used for the analyses of efficacy endpoints. The ITT population is considered as the primary population for efficacy analyses and the PP will be considered as supportive. If a subject receives an incorrect study treatment other than the intended study treatment, the analysis of that subject's data will be based on the actual treatment received for the safety and PP analyses and the randomized assignment for the ITT analyses. If a subject receives more than 1 study treatment, the treatment group assignment for the safety and PP analyses will be determined on a case by case basis.

- Pharmacokinetic (PK) population: All subjects who undergo plasma PK sampling and have evaluable concentration-time data for analysis will be included in the PK population. A sample that is below the limit of quantification (BLQ) of the assay is considered evaluable.

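### SAP 12.4 counts doses from the diary alone but divides by every treatment day; unless supervised clinic doses also reach the diary, compliance is understated by about 4.8 points over 84 days

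*SAP*

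**What the plan says.** **Numerator.** SAP 12.4 defines "Number of doses administered, calculated from the subject dose diary". Where a diary is not returned, or comes back with dosing records missing, "the number of doses taken during that period is assumed to be 0".

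**Denominator.** The same section gives "Total number of days exposed, defined as date of last dose of study drug minus date of first dose of study drug plus 1", so clinic days are included. The ratio follows: "Percent compliance will be calculated as the number of doses administered over the number of days exposed".

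**Clinic days.** The row "Study drug application under supervision" in Protocol Table 1 is marked at Baseline and Weeks 2, 4 and 8, and not at Week 12. Footnote q states: "On study visit days, subjects will not complete the diary at home; application time and NRS will be recorded in the clinic". Protocol 5.4 adds: "The date and time of each dose administered in the clinic will be recorded in the source documents".

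**Use of the result.** SAP 12.4 calls a subject compliant at 80% or more. SAP 8 lists, among criteria that may exclude a subject from the Per-Protocol (PP) population, "Failure to be compliant with treatment regimen (as defined in Section 12.4, i.e., compliance < 80" percent. The same section makes PP supportive to ITT and settles its membership in blinded review.

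**The concern.** The two halves of the ratio come from different sets of days. The denominator covers every day between first and last dose. The numerator covers only days with a diary entry, and the protocol points clinic-day doses to a different record. Read literally, four doses that site staff watched being applied are scored as missed.

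Two outputs depend on this ratio. One is the compliance summary by treatment group. The other is the 80% criterion, which feeds PP membership, the tabulated reasons for PP exclusion (SAP 12.1) and the PP analyses of the primary and secondary endpoints (SAP 12.8).

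**Working it through.** The documents state no expected compliance rate, so there is no figure to reproduce; 80% is a chosen threshold.

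**Inputs**
- Days exposed, D: 84 for 12 weeks of once-daily dosing, Day 1 to Day 84. This is nominal. I also checked 82 to 87 because visit dates can move.
- Supervised clinic doses, c: 4 (Protocol Table 1).
- True doses taken, T, including all four clinic doses.
- Cut-off: 80% (SAP 8 and 12.4).
- Assumption: clinic doses are not also in the diary.

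**Step 1: size of the understatement.** The rule as written gives (T − c)/D; counting every dose gives T/D. The difference is c/D = 4/84 = 4.8 percentage points (4/87 = 4.6 to 4/82 = 4.9).

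**Step 2: the fully adherent subject.** With T = 84 and all diaries returned, the score is 80/84 = 95.2% instead of 100%. Over the range of D it is 78/82 = 95.1% to 83/87 = 95.4%. This subject passes easily.

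**Step 3: the effective cut-off.** T/84 ≥ 0.80 requires T ≥ 67.2, so 68 doses. (T − 4)/84 ≥ 0.80 requires T ≥ 71.2, so 72 doses.

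| True doses | Missed | True compliance | Score as written |
|---|---|---|---|
| 68 | 16 | 81.0% | 64/84 = 76.2% |
| 69 | 15 | 82.1% | 65/84 = 77.4% |
| 70 | 14 | 83.3% | 66/84 = 78.6% |
| 71 | 13 | 84.5% | 67/84 = 79.8% |
| 72 | 12 | 85.7% | 68/84 = 81.0% |

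The counts 68 to 71 change status. In percentage terms the cut-off moves from 80% to 80% + 4.8 = 84.8% of true compliance. At each D from 82 to 87, exactly four dose counts are misclassified.

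**Step 4: one lost diary, otherwise perfect adherence.** A two-week diary covers 13 home doses (Days 2 to 14, or 16 to 28), which the zero rule removes.
- As written: (84 − 4 − 13)/84 = 67/84 = 79.8%, a fail.
- With clinic doses counted: (84 − 13)/84 = 71/84 = 84.5%, a pass.

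This case sits on the line: at D = 85 the score as written is 68/85 = 80.0%, which passes. A lost four-week diary (27 home doses) fails under both rules: 53/84 = 63.1% and 57/84 = 67.9%.

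**Step 5: early stoppers with perfect adherence.** The loss in points is larger over a short exposure, but the score stays high: 13/14 = 92.9% at 14 days, 13/15 = 86.7% at 15 days and 26/29 = 89.7% at 29 days. It is below 80% only at 4 days or fewer (3/4 = 75%; 4/5 = 80% passes).

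**The case against.** The strongest objection is that the omission is not established. Footnote q says only that the diary is not completed at home on visit days. Protocol 5.1.5 and 5.4 ask subjects to record the time of application in the diary without exempting clinic doses. The diary is on site at Weeks 2, 4 and 8, when it is collected and reissued, and is issued at Baseline. The explicit instruction in Protocol 6.2.2.4 not to use the diary on clinic days covers the itch score alone. SAP 12.8.3 expects that some clinic-day diary entries will exist. Staff may therefore enter clinic doses there.

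That stands as a condition on the finding, but it does not remove it. Footnote q names application time together with the itch score as recorded in the clinic, and Protocol 5.4 places clinic doses in source documents. SAP 12.8.3 says which source prevails when itch scores from diary and clinic share a date; SAP 12.4 has no such rule for doses. The literal rule still gives the wrong count wherever the diary lacks the clinic dose.

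Three stronger readings might be inferred, and the documents support none of them:
- *Compliant subjects in general fall below 80%.* Step 2 shows that they do not. The affected band is about 5 points wide, and without a compliance distribution the number in it is unknown and may be close to zero.
- *Early stoppers are wrongly removed from PP by the compliance rule.* They pass after 5 or more days of full adherence, and would in any case lack the Week 12 assessment that SAP 8 lists as a separate criterion.
- *The efficacy conclusions are biased.* The primary and sequential secondary tests use ITT with multiple imputation. The same counting rule applies in both arms, and nothing in the documents points to a differential effect.

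**Conclusion.** The point holds in a limited form. As written, SAP 12.4 puts clinic days in the denominator without a rule that puts their doses in the numerator. If the diary does not hold those doses, compliance is understated by about 4.8 points over 84 days, and the PP criterion works at about 84.8% true compliance rather than 80%. Those wrongly scored below 80% are subjects with 68 to 71 true doses of 84, and a fully adherent subject who loses one two-week diary at 84 days exposed.

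This rests on four supervised doses all taken, nominal visit days, and no clinic-day entry in the diary. The compliance summary would be wrong for subjects dosed in clinic. PP membership would be wrong only near the cut-off, and that criterion is permissive and reviewed blind. The matter is worth correcting because a reported figure is affected, but it does not threaten the primary result.

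**What to change.** In SAP 12.4, define doses administered as the number of calendar days, from first to last dose, on which a dose is recorded either in the diary or in the clinic record of supervised application. Count each day once, so that a dose in both records cannot push compliance above 100%. Use actual rather than nominal visit dates, because visits have a ±2-day window, and credit no supervised dose where the visit was missed or remote (SAP 12.11). Keep days exposed as the denominator. Apply the definition before the blinded PP review.

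Dropping clinic days from both numerator and denominator also removes the mismatch, but it is not identical near the cut-off: 68 true doses gives 64/80 = 80.0%, against 68/84 = 81.0%.

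The cost is one sentence of SAP text, a small amount of programming, and confirmation that the clinic dose dates are available in the database. Protocol 5.4 places them in source documents and does not say that they are captured in the eCRF.

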## **12.5 Prior and Concomitant Medications**

Prior (within the 34 days before Visit 1 and with stop dates prior to first dose of study drug) and concomitant (ongoing or with stop dates on or after first dose of study drug) medications will be listed by subject for each treatment group. If the medication is ongoing or the stop year is missing, the medication will be considered as received for the entire duration of the study. Medications will be coded using WHO-DD terminology.

To distinguish prior vs concomitant medications, the following rules for stop dates will apply:

- If only year was recorded, and it is before Baseline, it is a prior medication; if year is same or after Baseline, it is assumed to be a concomitant medication.
- If day is missing, but month and year are before Baseline, it is a prior medication; if month and year are the same as Baseline, it is assumed to be a concomitant medication; if month and year are after Baseline, it is a concomitant medication.
- If start date is after Baseline, it is a concomitant medication regardless.

Prior and concomitant medications will be summarized separately by treatment, WHO-DD Anatomical-Therapeutic-Chemical (ATC) classification and preferred term (PT).

## **12.6 Medical History and Concurrent Procedures**

Medical history (including previous and ongoing medical conditions) will be coded using MedDRA and listed by subject. Medical history will be summarized by system organ class (SOC) and PT for each treatment.

Psoriasis History, Cardiovascular Risk Factors and Liver Disease Family History will be summarized and listed by subject separately.

The following will be summarized by treatment group for psoriasis history:

- Duration (year) of disease, defined as year of Screening visit minus year of initial psoriasis diagnosis. Duration of disease will be reported as <5, 5-10, and >10 years for summary purpose.
- Area affected (scalp, pam, fingernails, toenails, soles)

## **12.7 Efficacy Endpoints**

### **12.7.1 Primary Efficacy Endpoint**

The primary efficacy endpoint is the proportion of subjects who achieve a Physician Global Assessment (PGA) treatment response, defined as a PGA score of clear (0) or almost clear (1) with a minimum 2-grade improvement from Baseline at Week 12.

The PGA is a static 5-point assessment of overall disease severity, as determined by the Investigator, ranging from 0 (clear) to 4 (severe).

### **12.7.2 Secondary Efficacy Endpoints**

The secondary endpoints are:

- Proportion of subjects with  $\geq 75\%$  improvement in Psoriasis Area and Severity Index from Baseline (PASI-75) at Week 12
- Proportion of subjects with a PGA score of 0 or 1 at Week 12
- Mean change in percent of total body surface area (%BSA) affected from Baseline to Week 12
- Proportion of subjects with  $\geq 90\%$  improvement in PASI score from Baseline (PASI-90) to Week 12.

The PASI score assesses the severity of psoriasis taking into account the overall severity of erythema (redness), induration (plaque thickness), and scale, and the extent of %BSA affected with psoriasis. The 3 clinical signs are each graded on a 5-point scale (0 to 4) and the %BSA affected is scored on a 7-point scale (0 to 6) for each of the 4 specified body regions (head, upper extremities, trunk, and lower extremities). The individual scores are multiplied by a weighted factor for each body region; the sum of these scores gives the overall PASI score.

